Research Protocol: A Comparative Study of the Advantages of Water-Separation Circumcision

Study Title: Comparative Evaluation of Hydrodissection circumcision vs. Traditional Circumcision Techniques: A Randomized Controlled Trial

1. Study Objective: The objective of this study is to compare the clinical outcomes and advantages of water-separation circumcision (Group A) versus two traditional circumcision techniques (Group B: "Subcutaneous Tissue Sparing "and Group C: "Non-Subcutaneous Tissue Sparing ") in male patients.

2. Background and Rationale: Circumcision is one of the most commonly performed surgical procedures globally. Several techniques exist, including those that preserve or remove subcutaneous tissues. A newer method, water-separation circumcision, is being introduced as a potential improvement. This study aims to evaluate its effectiveness in terms of complications, healing time, and patient satisfaction, comparing it with traditional circumcision techniques.

3. Study Design: This is a **prospective, randomized controlled trial** designed to evaluate the clinical outcomes of water-separation circumcision (Group A) compared to two traditional circumcision techniques (Group B and Group C).

4. Inclusion Criteria:

- ① Complies with the diagnostic criteria for phimosis, foreskin elongation, and related diseases in the "Chinese Expert Consensus on Phimosis, Foreskin related Diseases";
- ② Preoperative routine examination showed no abnormalities in coagulation, blood routine, electrocardiogram and other indicators;
- ③ No severe genital herpes, gonorrhea, syphilis, glans infection, etc.;
- ④ Complies with the indications for sleeve type circumcision;
- ⑤ The patient or family member is aware of the surgical plan and signs the informed consent form.

5. Exclusion Criteria:

- ① Patients with concomitant urethral malformations, such as hypospadias;
- ② Patients with combined inflammation of the penis, prior penile surgery, severe adhesions, buried penis, and short frenulum of the penis;
- ③ Exclude individuals with combined allergies or allergies to multiple medications;
- ④ Patients with severe physical illnesses such as heart and lung dysfunction who cannot tolerate surgery;

- ⑤ Individuals with cognitive impairments or mental abnormalities;
- ⑥ Diabetes with poor glycemic control;
- ⑦ Age >35 or Age<6.

6. Intervention Groups:

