Group A (Hydrodissection circumcision): This group will undergo the water-separation circumcision technique, where water is used to separate the skin from the underlying tissues before performing the circumcision (HC).

Group B (Subcutaneous Tissue Sparing Circumcision):

This group will undergo a traditional circumcision procedure where the subcutaneous tissue is preserved, aiming for less scarring and quicker healing (sCC).

Group C (Non-Subcutaneous Tissue Sparing Circumcision):

This group will undergo the traditional circumcision procedure in which the subcutaneous tissue is not sparing (uCC).

7. Outcome Measures:

Primary Outcome Measure:

1. operation time

Operative time was calculated by timer.

[Time Frame: 1 day]

2. intraoperative bleeding

The amount of intraoperative bleeding is calculated by weighing gauze before and after operation. 1 milliliter is approximately equal to the weight of 1 gram.

[Time Frame: 1 day]

3. The healing time

The healing time was judged by the doctors based on the observation of the wound and inquiry of the patients during 7-25 days after surgery. We defined complete wound healing as the absence of a scab with a completely epithelialized and dry skin surface based on clinical assessment.

[Time Frame: 7-25 days]

4. Intra-operative pain

Intra-operative pain was graded immediately after the operation while the post-operation pain was graded at 1 week by NRS (Numeric Rating Scale). The scale typically ranges from 0 to 10. 0 indicates no pain, while 10 signifies the most severe pain imaginable.

[Time Frame: 1 day]

Secondary Outcome Measures:

5. other complications

incidence rate

[Time Frame: through study completion, an average of 1 year]

6. patient satisfaction

Patient satisfaction is divided into 5 levels: Extremely dissatisfied, Dissatisfied, Neutral, Satisfied, Extremely Satisfied.

[Time Frame: through study completion, an average of 1 year]

8. Sample Size Calculation:

Given an assumed type I error (α) of 0.05 and type II error (β) of 0.20, a power of 80% is desired to detect a significant difference in the primary outcome (complication rate). Using a conservative estimate based on previous studies of circumcision complication rates, a sample size of 96 patients (32 patients per group) will provide sufficient power to detect differences between the three techniques.

This sample size assumes a 10% dropout rate, so 96 patients will be recruited in total.

9. Randomization:

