Randomization will be performed using a computer-generated randomization list, ensuring that each participant has an equal chance of being assigned to one of the three groups. Stratified randomization

will be used to ensure balance across demographic variables (e.g., age, baseline health status). Patients will be blinded to group assignment, and the surgical team will remain unaware of the group allocation to reduce bias.

10. Statistical Analysis:

Data will be analyzed using the **Statistical Package for the Social Sciences (SPSS)** software, version 26 (or newer). The following statistical methods will be applied:

Descriptive statistics (mean, standard deviation, frequency distributions) will be used for demographic data and outcome measures.

Chi-square tests will be used to compare categorical variables (e.g., complication rates between the three groups).

Analysis of variance (ANOVA) will be applied to compare continuous variables (e.g., healing time, pain scores) between groups.

If assumptions of normality are violated, **Kruskal-Wallis tests** (non-parametric version of ANOVA) will be used.

Post-hoc tests (e.g., Tukey's test) will be applied where significant differences are found in the ANOVA. **Kaplan-Meier survival analysis** will be used to assess time to healing (i.e., complete wound closure). **P-values of < 0.05** will be considered statistically

significant. **Confidence intervals (95%)** will be reported for all continuous outcomes.

11. Ethical Considerations: The study will be conducted in accordance with the **Declaration of Helsinki** and will be approved by the Chongqing Jiulongpo Hospital ethics committee. All patients will provide written informed consent prior to participation, and their rights, confidentiality, and well-being will be ensured throughout the study. The clinical trial will be registered in a public database.

12. Timeline:

Study start date: 2019-6-30

Study end date: 2024-2-07

Recruitment period: 3 months

Follow-up period: 1 year after surgery

13. Budget Considerations:

Personnel costs (surgeons, nurses, data managers):

1000 x 96=96000RMB

Materials and Equipment (surgical tools, sutures, bandages, anesthesia)

500 x 96=48000RMB

Statistical and software tools: 1000 RMB

Participant compensation for time and travel:

1000 X96=96000 RMB

Principal Investigator: [[name]]

Study Coordinators: [[name]]

Contact Information: [Department of Urology,

Peking University First Hospital, 86

[name]]

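### Complications get one three-group chi-square P-value, with no A-B or A-C difference and no interval, although the objective is A against B and A against C

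*Protocol*

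**What the plan says.** Section 10 contains the Protocol's only statement on confidence intervals: 95% intervals "will be reported for all continuous outcomes". For categorical data it says "Chi-square tests will be used to compare categorical variables (e.g., complication rates between the three groups", and the significance rule is "P-values of < 0.05". Post-hoc tests are planned where the ANOVA shows a difference; none is planned after a chi-square test. Section 10 also plans frequency distributions for outcome measures.

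The status of complications varies by section. Section 2 says the trial will "evaluate its effectiveness in terms of complications, healing time, and patient satisfaction". Section 7 lists "5. other complications" among the secondary outcomes, measured as an "incidence rate". Section 8 sizes the trial to detect "a significant difference in the primary outcome (complication rate"). Section 1 sets the objective as Group A compared with Groups B and C.

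**The concern.** The objective calls for two contrasts, A with B and A with C. For complications the plan provides a single test that all three rates are equal. That test does not say which technique differs, in which direction or by how much, and no pairwise step follows it. The interval commitment covers the outcomes on which an advantage for Group A is most likely to be shown (operation time, bleeding, healing time) but not the outcome on which harm would appear.

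At stake is what can be concluded about complications. The trial could report a shorter operation or less bleeding for Group A next to a non-significant complication test, and nothing in the planned output would show how large an excess the data still allow.

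**Working it through.** **Inputs.** From the Protocol: 96 patients, 32 per group, 10% dropout and α 0.05 (Section 8); chi-square test at P<0.05 (Section 10). With dropout, 32 × 0.9 = 28.8, or about 29 evaluable per group. The Protocol states no complication rate and no difference to be detected. All rates and event counts below are therefore assumptions, and the 32 per group for 80% power cannot be reproduced.

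**1. What the planned test can detect.** Two arms have complication rate p and one arm has p + d. All outcomes (i, j, k) are enumerated with their binomial probabilities. With m = (i + j + k)/3, the test rejects when [(i−m)² + (j−m)² + (k−m)²] × [1/m + 1/(n−m)] exceeds 5.991, the 5% point of chi-square on 2 degrees of freedom.

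| p in the other two arms | d = 10 points, n = 32 | d = 10, n = 29 | d = 15 points, n = 32 | d = 15, n = 29 |
|---|---|---|---|---|
| 2% | 38% | 35% | 64% | 59% |
| 5% | 26% | 23% | 49% | 44% |
| 10% | 20% | 18% | 38% | 34% |
| 15% | 17% | 15% | 32% | 29% |

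For a 20-point excess at 32 per arm, power is about 50-83% over the same rates.

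**2. What an interval would show.** The Newcombe interval for p₁ − p₂ uses the Wilson limits (l, u) of each proportion:

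- lower = (p₁ − p₂) − √[(p₁ − l₁)² + (u₂ − p₂)²]
- upper = (p₁ − p₂) + √[(u₁ − p₁)² + (p₂ − l₂)²]

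Equal counts at 32 per arm:

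- 0 v 0: the Wilson upper limit is z²/(n + z²) = 3.8415/35.8415 = 0.107, so the interval is ±10.7 points.
- 2 v 2: p = 0.0625, Wilson limits 0.0173 and 0.2015; √(0.1390² + 0.0452²) = 0.146, so ±14.6 points.
- 3 v 3: ±16.1 points.

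At 29 per arm the same counts give ±11.7, ±15.9 and ±17.4 points.

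**3. An example with Group A worse.** Assume 5 events in A and 2 in each of B and C, with 32 per arm.

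- Planned test: every arm has expected counts of 3 and 29. X² = (2² + 1² + 1²) × (1/3 + 1/29) = 6 × 0.3678 = 2.207; on 2 degrees of freedom, P = exp(−2.207/2) = 0.33.
- A minus B: p₁ = 0.1563 (Wilson 0.0686 to 0.3175), p₂ = 0.0625 (0.0173 to 0.2015), difference 0.0938.
- Lower: 0.0938 − √(0.0876² + 0.1390²) = 0.0938 − 0.1643 = −0.0705.
- Upper: 0.0938 + √(0.1613² + 0.0452²) = 0.0938 + 0.1675 = 0.2613.

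The planned report would show 5, 2 and 2 events and P = 0.33. The interval, −7.1 to +26.1 points, shows that a large excess for A has not been ruled out.

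**The case against.** The strongest reply is that the effect measure and interval method are ordinary analysis-plan detail, that an analysis plan may exist unseen, and that Section 10 promises intervals for continuous outcomes without forbidding them elsewhere. It is true that nothing is forbidden and that an analysis plan could add intervals. But the Protocol is not silent: it addresses intervals, states their scope, ties pairwise comparisons to the ANOVA, and so leaves out the outcome it was sized on.

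Four stronger readings are tempting, and the documents do not support them.

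- A reader might infer that the test will be non-significant whatever the truth. It will not. Power reaches about 50-83% for a 20-point excess, and from a 5% rate it is about 94% for 30 points. Even at 15 points it passes one half when the other arms are at 2%. The weakness concerns excesses of about 10 points, and of 15 points when the other arms are at 5% or more.
- A reader might infer that the plan gives no information on the size of any excess. Frequencies by arm are planned, and a reader could compute a difference and interval from them. What is missing is a planned contrast and a reported interval.
- A reader might blame the missing interval for the imprecision. The imprecision comes from about 30 patients per arm.
- A reader might infer that the Protocol will call P>0.05 equal safety. It nowhere says so, and no equivalence or non-inferiority claim is planned.

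**Conclusion.** The point holds as a correctable weakness in how complications are analysed and reported. It does not by itself call for a redesign. Whichever label applies to complications (Sections 7 and 8 disagree), the planned output does not answer the A-B and A-C questions in the objective.

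The size depends on assumptions, because the Protocol states no rates. Over assumed rates of 2-15%, a non-significant chi-square would be weak evidence against an excess of 10 to 15 points in one arm. With identical observed counts of 0 to 3 per arm, the pairwise limits run from about 11 to 16 points at 32 per arm and about 12 to 17 at 29; they widen further with more events.

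**What to change.** In Section 10, change the interval sentence so that 95% confidence intervals cover categorical as well as continuous outcomes. Add that complications will be reported as A-B and A-C risk differences with Newcombe (or Miettinen-Nurminen) 95% intervals, beside the three-group chi-square result.

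The cost is one amended sentence, two extra table rows and possibly a calculation outside the standard SPSS output. No extra patients or data are needed. The intervals will be wide; they let readers see the imprecision but do not cure it.
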